### 3.7.2. Analysis Visit Windows

Subject visits might not occur on protocol-specified days. Therefore, for the purpose of analysis, observations will be assigned to analysis windows.

The analysis windows for HIV-1 RNA and VAS are provided in [Table 3-1](#).

**Table 3-1. Analysis Visit Windows for HIV-1 RNA and VAS**

Nominal Visit	Nominal Day	Lower Limit	Upper Limit
Baseline	1	(none)	1
Week 4	28	2	42
Week 8	56	43	70
Week 12	84	71	98
Week 16	112	99	140
Week 24	168	141	210
Week 36	252	211	294
Week 48	336	295	378

The analysis windows for CD4+ cell count, CD4%, hematology, chemistry, urinalysis, urine chemistry laboratory tests, eGFRCG, vital signs and weight, are provided in [Table 3-2](#).

**Table 3-2. Analysis Visit Windows for CD4+ Cell Count, CD4%, Hematology, Chemistry, Urinalysis, Urine Chemistry Laboratory Tests, eGFRCG, Vital Signs and Weight**

Nominal Visit	Nominal Day	Lower Limit	Upper Limit
Baseline	1	(none)	1
Week 4	28	2	42
Week 8	56	43	70
Week 12	84	71	126
Week 24	168	127	210
Week 36	252	211	294
Week 48	336	295	378

The analysis windows for fasting glucose, lipid panels, EQ-5D, SF-36, and FACIT-F are provided in [Table 3-3](#).

**Table 3-3. Analysis Visit Windows for Fasting Glucose, Lipid Panels, EQ-5D, SF-36, and FACIT-F**

Nominal Visit	Nominal Day	Lower Limit	Upper Limit
Baseline	1	(none)	1
Week 24	168	2	252
Week 48	336	253	420

Lipid panel includes total cholesterol, HDL, direct LDL and triglycerides.

The analysis windows for ECG are provided in [Table 3-4](#).

**Table 3-4. Analysis Visit Windows for ECG**

Nominal Visit	Nominal Day	Lower Limit	Upper Limit
Baseline	1	(none)	1
Week 48	336	2	671

The analysis windows for HIVTSQs (at Day 1 Only) and HIVTSQc are provided in [Table 3-5](#).

**Table 3-5. Analysis Visit Windows for HIVTSQs (at Day 1 Only) and HIVTSQc**

Nominal Visit	Nominal Day	Lower Limit	Upper Limit
Baseline	1	(none)	1
Week 4	28	2	98
Week 24	168	99	252
Week 48	336	253	420

### 3.7.3. Selection of Data in the Event of Multiple Records in an Analysis Visit Window

Depending on the statistical analysis method, single values may be required for each analysis window. For example, change from baseline by visit usually requires a single value, whereas a time-to-event analysis would not require one value per analysis window. When a single value is needed, the following rule(s) will be used:

If multiple nonmissing numeric observations exist in a window, records will be chosen as follows:

- For baseline, the last available record on or prior to the date of the first dose of study drug will be selected. If there are multiple records with the same time or no time recorded on the same day, average (geometric mean for HIV-1 RNA and arithmetic mean for others) will be computed for that day.
- For postbaseline visits:

For key efficacy and safety data (ie, HIV-1 RNA level, CD4+ cell count, and CD4%), the latest record in the window will be selected.

For other numeric observations, the record closest to the nominal day for that visit will be selected. If there are 2 records equidistant from the nominal day, the latest will be selected.

If there is more than 1 record on the selected day, the average will be taken (geometric mean for HIV-1 RNA and arithmetic mean for others).

If multiple nonmissing categorical observations (eg, safety ECG results) exist in a window, records will be chosen as follows:

- For baseline, the last available record on or prior to the date of the first dose of the study drug will be selected. If there are multiple records with the same time or no time recorded on the same day, the value with the lowest severity will be selected (eg, normal will be selected over abnormal for safety ECG findings).
- For postbaseline visits, the most conservative value within the window will be selected (eg, abnormal will be selected over normal for safety ECG)

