3.3. Duration of Treatment

The study will consist of a 42-day screening period (within 42 days before Day 1 visit), followed by a 48 week treatment period. After Day 1, subjects will return for study visits at Weeks 4, 8, 12, 16, 24, 36 and 48.

After Week 48, subjects will stop study drug and complete a 30-Day Follow-up visit.

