Subjects who complete the study through the Week 48 visit will be required to return to the clinic 30 days after the completion of study drugs for the 30-Day Follow-Up Visit.

Subjects who permanently discontinue study drug and refuse to continue study visits through Week 48 will be asked to return to the clinic after the completion of the ESDD visit for a 30-Day Follow-Up visit.

Those subjects who permanently discontinue study drug and continue in the study through at least one subsequent visit after the Early Study Drug Discontinuation Visit will not be required to complete the 30-Day Follow-Up Visit.

For the purpose of scheduling a 30-Day Follow-Up Visit, a ± 6 days window may be used. The following evaluations are to be completed at the 30-Day Follow-Up Visit:

- Review of AEs and changes in concomitant medications
- Symptom-directed physical examination as needed
- Vital signs (blood pressure, pulse, respiration rate, and temperature), including weight
- Urine collection for the following laboratory procedures:
 - Urinalysis and urine chemistry
- Blood sample collection for the following laboratory analyses:
 - Chemistry profile: alkaline phosphatase, AST, ALT, total bilirubin, direct and indirect bilirubin, total protein, albumin, bicarbonate, BUN, calcium, chloride, creatinine, glucose, potassium and sodium

- Hematology profile: CBC with differential and platelet count
- Plasma HIV-1 RNA
- CD4+ cell count

At the 30-Day Follow Up Visit, any evaluations showing abnormal results believed to be a reasonable possibility of a causal relationship with the study drug will be repeated weekly (or as often as deemed prudent by the Investigator) until the abnormality is resolved, returns to baseline, or is otherwise explained.

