##### **3.1.2. Full Analysis Set**

The Full Analysis Set (FAS) will include all the subjects who were enrolled and received at least one dose of study drug. For the FAS, all efficacy data will be included, unless specified otherwise. The FAS is the primary analysis set for the efficacy analyses.

Subjects meeting the following criteria will be excluded from the FAS:

- Subjects who took Stribild or Descovy as part of the baseline antiretroviral (ARV) regimen and thus violated the inclusion criterion.

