##### **6.2.2.2. Time to Pure Virologic Failure Analysis**

For subjects who do not experience a confirmed rebound (ie, HIV-1 RNA  $\geq$  50 copies/mL on 2 consecutive visits or the last available HIV-1 RNA  $\geq$  50 copies/mL followed by premature discontinuation of study), subjects will be censored at the last HIV-1 RNA collection date. For subjects who experience confirmed rebound, the time to PVF will be defined as the earlier time of 2 consecutive HIV-1 RNA  $\geq$  50 copies/mL or the last available HIV-1 RNA  $\geq$  50 copies/mL followed by premature discontinuation of study.

Time to PVF will be analyzed using the KM method by Part 1 and Part 2 using the FAS.

Lastly, subjects who failed according to snapshot algorithm, pure virologic failure analysis algorithms, or had premature study drug discontinuation by Week 48 will be listed.

6.2.2.3. Analysis of proportion of subjects with HIV-1 RNA < 50 copies/mL at Weeks 12, 24, and 48 as determined by the US FDA-defined snapshot algorithm

The analysis windows for Weeks 12, 24, and 48 are defined in [Table 3-1](#). All HIV-1 RNA data collected on-treatment (eg, data collected up to 1 day after the last dose date of study drug) will be used in the US FDA-defined snapshot algorithm. Virologic outcome will be defined as the following categories:

- **HIV-1 RNA < 50 copies/mL:** this includes subjects who have the last available on-treatment HIV-1 RNA < 50 copies/mL in the analysis window
- **HIV-1 RNA ≥ 50 copies/mL:** this includes subjects:
  - a. Who have the last available on-treatment HIV-1 RNA ≥ 50 copies/mL in the analysis window, or
  - b. Who do not have on-treatment HIV-1 RNA data in the analysis window and
    - 1) Who discontinue study drug prior to or in the analysis window due to lack of efficacy (note: Lack of efficacy is defined as having the check-box for Lack of efficacy marked on the Study Drug Completion eCRF), or
    - 2) Who discontinue study drug prior to or in the analysis window due to AE or death and have the last available on-treatment HIV-1 RNA ≥ 50 copies/mL
    - 3) Who discontinue study drug prior to or in the analysis window due to reasons other than AE, death, or lack of efficacy and have the last available on-treatment HIV-1 RNA ≥ 50 copies/mL
- **No Virologic Data (in the Window):** this includes subjects who do not have on-treatment HIV-1 RNA data in the analysis window because of the following:

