6.2.2.5. Analysis of Proportion of Subjects with HIV-1 RNA  $< 50$  copies/mL  
(Missing Excluded and Missing Failure Approaches)

The proportion of subjects with HIV-1 RNA  $< 50$  copies/mL will also be analyzed using the following 2 methods for imputing missing HIV-1 RNA values, where the proportions will be expressed as percentages in all tables, listings, and figures:

- Missing Failure (M F)

In this approach, all missing data will be treated as HIV-1 RNA  $\geq 50$  copies/mL. The denominator for percentages at a visit is based on the number of subjects in the FAS.

- Missing Excluded (M E)

In this approach, all missing data will be excluded in the computation of the proportions (ie, missing data points will be excluded from both the numerator and denominator). The denominator for percentages at a visit is based on the number of subjects in the FAS with non-missing HIV-1 RNA value at that visit.

For both M F and M E analyses, the number and percentage of subjects with HIV-1 RNA in the following categories will be summarized:

- $< 50$  copies/mL
- $< 20$  copies/mL
  - $< 20$  copies/mL Not Detectable
  - $< 20$  copies/mL Detectable

- 20 to < 50 copies/mL
- $\geq 50$  copies/mL
- Missing (only applicable for M F analysis)

The proportion of subjects with HIV-1 RNA < 50 copies/mL as defined by the 2 different missing data imputation methods will be summarized for each visit. Two-sided 95% CIs will be constructed using the exact method.

For M F analysis, results will be summarized and plotted for visits up to and including Week 12. For M E analysis, results will be summarized for each visit.

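### In the Week 48 Missing = Excluded analysis, the window and latest-record rules select the off-drug 30-Day Follow-up HIV-1 RNA instead of the Week 48 sample

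*SAP*

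**What the plan says.** The point comes from reading several rules together.

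- **Drug stops at Week 48.** Protocol 3.3: "After Week 48, subjects will stop study drug and complete a 30-Day Follow-up visit".
- **HIV-1 RNA is drawn again off drug.** Under Protocol 6.4.2, completers must "return to the clinic 30 days after the completion of study drugs for the 30-Day Follow-Up Visit", with a scheduling tolerance of ± 6 days. Plasma HIV-1 RNA is on the list for that visit and is marked in the follow-up column of both schedules (Protocol Appendix 2, SAP Appendix 1).
- **Records are placed by study day.** SAP 3.7.2 assigns observations to analysis windows. The last row of SAP Table 3-1 reads "Week 48 336 295 378" (nominal day, lower limit, upper limit). The table has no row for the follow-up visit.
- **One record per window.** For HIV-1 RNA after baseline, SAP 3.7.3 says "the latest record in the window will be selected".
- **Data scope.** SAP 3.1.2: "For the FAS, all efficacy data will be included, unless specified otherwise". The snapshot analysis (SAP 6.2.2.3) does specify otherwise: "All HIV-1 RNA data collected on-treatment (eg, data collected up to 1 day after the last dose date of study drug". CD4+ count and CD4% (SAP 6.2.2.6 and 6.2.2.7) carry the same limit.
- **Missing = Excluded (M=E).** SAP 6.2.2.5 sets the denominator as FAS subjects "with non-missing HIV-1 RNA value at that visit" and states no on-treatment limit. M=E is summarized at every visit, so Week 48 is included. Missing = Failure (M=F) is summarized only through Week 12.

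**The concern.** M=E should differ from the snapshot only in how it treats missing values. Under these rules it also differs in treatment status. At Week 48 it would report viral load about a month after E/C/F/TAF ended, under a label that reads as a result on the drug.

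A subject who was viraemic on drug at Week 48 and suppressed at follow-up would count as below 50 copies/mL; the reverse pattern would count as 50 or above. SAP 6.2.1 lists this proportion among the secondary efficacy endpoints and SAP 6.2.2.5 gives it an exact confidence interval, so a reader of the report would set it beside the Week 48 snapshot. A difference between the two could then come from the change of sample and not from missing data, and the table would not show which.

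**Working it through.** **Inputs**
- Week 48 nominal day 336, window 295 to 378 (SAP Table 3-1).
- Week 48 visit: scheduling tolerance ± 6 days, permitted window ± 6 weeks (Protocol 6.3.1).
- Follow-up: 30 days after completing drug, ± 6 days (Protocol 6.4.2).
- Sample size 64 after the reduction (SAP 1.3).
- Assumption: the last dose is taken on the day of the Week 48 visit.

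**Reproducing the plan's window.** 336 + 42 = 378, which matches the stated upper limit. 336 − 42 = 294; that day belongs to the Week 36 window, so Week 48 starts at 295. The table agrees with the ± 6 weeks in the protocol.

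**Where the follow-up sample falls.** Follow-up day = Week 48 visit day + 30 ± 6.
- Nominal: 336 + 30 = 366, inside 295 to 378 and later than 336, so it is selected.
- Earliest on schedule: 330 + 24 = 354. Latest: 342 + 36 = 378.
- Of the 13 × 13 = 169 combinations of the two tolerances, 169 fall inside the window.
- If Week 48 is counted as study day 337 (336 days after Study Day 1), the range is 355 to 379 and 168 of 169 fall inside.
- The selected sample is 30 − 6 = 24 to 30 + 6 = 36 days after the last dose, well beyond the limit of last dose plus 1 day used for snapshot and CD4.

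**When the Week 48 sample survives.** The follow-up leaves the window when the Week 48 visit day exceeds 378 minus the interval:
- interval 30 days: after Day 348, which is 348 − 336 = 12 days late;
- interval 36 days: after Day 342;
- interval 24 days: after Day 354.

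Such visits are outside the scheduling tolerance, or at its edge, but inside the permitted ± 6 weeks. These completers, and those who miss follow-up, keep the Week 48 value.

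**Weight of one subject.** 1/64 = 1.6 percentage points. The documents give no rate of viraemia at follow-up, so the counts below are assumptions, with all 64 subjects observed:

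| Selected values ≥ 50 copies/mL (assumed) | Week 48 M=E | Exact 95% lower limit |
|---|---|---|
| 0 | 100% | 94.4% |
| 1 | 98.4% | 91.6% |
| 3 | 95.3% | 86.9% |
| 6 | 90.6% | 80.7% |
| 10 | 84.4% | 73.1% |

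The table shows how sensitive the figure is. It is not a forecast.

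**The case against.** The best defence is that little depends on this figure. The Week 12 primary endpoint and the durability objective both use pure virologic response, which rests on confirmed rebound and not on one selected record per window. An on-treatment snapshot at Week 48 will be reported alongside. The protocol's secondary endpoints do not name M=E, and no hypothesis is tested. All of this stands, and it limits the importance of the point.

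Two textual defences do not stand. SAP Appendix 5 item 25 defines on-treatment HIV-1 RNA, but SAP 6.2.2.5 never uses that term. SAP 1.2 leaves the follow-up out of its list of HIV-1 RNA visits, but SAP Appendix 1 and Protocol 6.4.2 both schedule the draw.

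A reader might infer three stronger claims that the documents do not support.
- **That M=F at Week 48 is equally affected.** SAP 6.2.1 does list both methods at Week 48, but SAP 6.2.2.5 plans M=F summaries only through Week 12.
- **That values after early drug discontinuation wrongly enter M=E or M=F at earlier visits.** Protocol 6.3.1 deliberately continues evaluations off drug and the FAS keeps all efficacy data. Using those values beside an on-treatment snapshot is a defensible choice.
- **That the result is biased in a known direction.** The documents do not say what therapy subjects take between Week 48 and follow-up; Protocol 3.5 leaves later care to the treating physician.

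**Conclusion.** The point holds for one analysis, the Week 48 M=E summary. Followed literally, the SAP takes the off-drug follow-up sample for every completer who attends both visits on schedule (all but one of 169 day combinations if Week 48 is counted as Day 337). Completers whose Week 48 visit is more than about 12 days late, or who miss follow-up, contribute on-drug values, so the percentage may be an unlabelled mixture. How much of each cannot be known before attendance is seen.

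The effect on the percentage is unknown in size and direction. This should be fixed because a stated rule picks the wrong sample, but it does not threaten the trial's main conclusions.

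**What to change.** State in SAP 3.7.3, in 6.2.2.5, or in both, that HIV-1 RNA from the 30-Day Follow-up visit is not assigned to the Week 48 window and is listed separately, so that Week 48 M=E uses the Week 48 sample.

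This is better than treating every off-drug value as missing in M=E. That broader rule would remove a subject who stopped drug while viraemic from numerator and denominator at later visits, and could raise the percentage.

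The cost is one or two sentences and a filter on visit, with no new data. A completer with a follow-up value but no Week 48 sample would become missing and leave the M=E denominator; the table should show that count. If the SAP is already final, its Section 1 provides for documenting the change in the clinical study report.

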6.8.1. Management of Virologic Failure

- If the viral load is ≥ 50 copies/mL, HIV-1 RNA should be repeated at a scheduled or unscheduled visit 2-4 weeks after the date of the original test with HIV-1 RNA ≥ 50 copies/mL.
- Upon confirmation of HIV-1 RNA ≥ 50 copies/mL, potential causes of virologic failure should be documented. Assessments should include:
 - Adherence
 - Concomitant medication
 - Comorbidities (for example: active substance abuse, depression, other intercurrent illnesses)
- Investigators should discuss the management of all subjects with confirmed virologic failure with the Medical Monitor.
- If virologic failure is confirmed at the scheduled or unscheduled visit and HIV-1 RNA is ≥ 50 copies/mL, the blood samples from the confirmation visit will be used for HIV-1 genotype/phenotype testing.

[figure not shown]
- If genotype/phenotype resistance to study drug is documented, study drugs should be discontinued.
- If no resistance is detected from genotype/phenotype testing, subject may remain on study drug and a repeat HIV-1 RNA should be repeated (2-4 weeks from the date of confirmed test with HIV-1 RNA \geq 50 copies/mL). Investigators should carefully evaluate the benefits and risks of remaining on study drug for each individual subject and document this assessment in the onsite medical record. Investigators who opt to discontinue study drugs for an individual subject must discuss with the Medical Monitor prior to study drug discontinuation.

Please refer to [Figure 6-1](#) for the management of subjects who meet the criteria for virologic failure.

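### Taking the latest HIV-1 RNA in each window classes the same isolated elevation differently by visit, and lets the off-drug 30-day sample stand for Week 48 in the Missing=Excluded table

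*SAP*

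**What the plan says.** - **Record selection.** SAP 3.7.3 says that where one HIV-1 RNA value per post-baseline window is needed, "the latest record in the window will be selected". For most other numeric data the same section takes the record closest to the nominal day.
- **Snapshot.** SAP 6.2.2.3 follows the same principle. Its success category reads "this includes subjects who have the last available on-treatment HIV-1 RNA < 50 copies/mL in the analysis window", with on-treatment data ending one day after last dose.
- **Windows.** SAP Table 3-1 ("Analysis Visit Windows for HIV-1 RNA and VAS") gives nominal day, lower limit and upper limit. Examples are "Week 12 84 71 98", "Week 16 112 99 140" and "Week 24 168 141 210".
- **Retest.** Protocol 6.8.1 says that after a value of 50 copies/mL or more, "HIV-1 RNA should be repeated at a scheduled or unscheduled visit 2-4 weeks after the date of the original test".
- **By-visit tables.** SAP 6.2.2.5 reports the proportion below 50 copies/mL visit by visit under both missing-data methods. It then limits Missing=Failure to visits through Week 12 and gives Missing=Excluded at every visit. It sets no on-treatment limit, and SAP 3.1.2 includes all efficacy data in the FAS unless specified otherwise.
- **End of treatment.** Protocol 3.3 stops study drug after Week 48. Protocol 6.4.2 takes a further HIV-1 RNA sample at the 30-Day Follow-up Visit.

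**The concern.** Each rule is reasonable alone. Together they make the classification of one event depend on the visit at which it occurs. Take a subject with a single value of 50 copies/mL or more that is below 50 on retest. At Week 12 the retest usually falls in the next window and the elevated value stands. At Week 24 the retest is in the same window, is the latest record, and replaces it. At Week 48 the retest is off drug and the snapshot cannot use it.

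There is no control arm in which the artefact would cancel, and with 64 subjects and a high response rate a few subjects shape the picture. A reader comparing snapshot results at Weeks 12, 24 and 48, or reading down the Missing=Excluded table, could take a window effect for a change in suppression.

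Missing=Excluded has a second problem. Because no on-treatment limit is set, a sample taken about a month after study drug ended can be the latest record in the Week 48 window.

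**Working it through.** The documents give no figure for this effect. Their only sizing figures reproduce: 1.96 × √(0.90 × 0.10/100) = 5.9% and 1.96 × √(0.95 × 0.05/64) = 5.3% (SAP 1.3). Nothing below depends on them.

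**Inputs.** Retest lag L is 14 to 28 days (Protocol 6.8.1). Visit deviation d is ±2 days through Week 16 and ±6 days afterwards (Protocol 6.3.1; for Week 48, the scheduling window). Room R is the upper limit minus the nominal day (SAP Table 3-1):

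- Weeks 4, 8, 12: 42 − 28 = 70 − 56 = 98 − 84 = 14
- Week 16: 140 − 112 = 28
- Weeks 24, 36, 48: 210 − 168 = 294 − 252 = 378 − 336 = 42

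The retest is in the same window when d + L ≤ R. SAP 3.7.1 counts the first dose as day 1, so a visit made exactly on schedule may fall one study day later; R then drops by 1. Both alignments are shown, with every permitted pair (d, L) weighted equally, which is an assumption.

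| Visit | In window | One day later |
|---|---|---|
| Weeks 4, 8, 12 | 6/75 = 8% | 3/75 = 4% |
| Week 16 | 72/75 = 96% | 69/75 = 92% |
| Weeks 24, 36 | 195/195 = 100% | 195/195 = 100% |
| Week 48, by calendar | 195/195 = 100% | 195/195 = 100% |
| Week 48, snapshot | 0% | 0% |

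At Week 12, for example, d = −2 allows L = 14, 15 or 16; d = −1 allows 14 or 15; d = 0 allows 14. That is 3 + 2 + 1 = 6 of 5 × 15 = 75. At Weeks 24 and 36 the largest d + L is 6 + 28 = 34, below 42 and 41. The snapshot share at Week 48 is zero because a retest at least 14 days after the visit is past last dose plus one day.

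**Sensitivity to retest timing.** If every retest is on day 14, the Week 4, 8 and 12 share is 3/5 = 60% (2/5 = 40% one day later). If every retest is on day 21, it is 0% at Weeks 4, 8 and 12 and 100% at Weeks 16, 24 and 36.

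**Size.** Expected subjects classed as 50 or more through transient elevation alone = 64 × rate × (1 − share). The rate is assumed.

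| Assumed rate | Week 12 (share 8%) | Week 24 | Week 48 snapshot |
|---|---|---|---|
| 1% | 0.6 | 0 | 0.6 |
| 3% | 1.8 | 0 | 1.9 |
| 5% | 2.9 | 0 | 3.2 |

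With all retests on day 14 and a 5% rate, Week 12 becomes 64 × 0.05 × 0.4 = 1.3 to 64 × 0.05 × 0.6 = 1.9. For scale, two such subjects move 64/64 (exact 95% CI 94.4-100%) to 62/64 (89.2-99.6%).

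**30-day sample.** With the Week 48 visit on day 336 ± 6, drug stopped at that visit, and follow-up 30 ± 6 days later (Protocol 6.4.2), the sample falls on days 354 to 378. The Week 48 window is 295 to 378, so all 13 × 13 = 169 combinations are inside. One day later, the range is 355 to 379 and 168/169 = 99.4% are inside. Protocol 6.3.1 also permits a Week 48 visit up to six weeks late; after a visit later than day 354, even the earliest follow-up (24 days on) misses the window.

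**The case against.** The strongest reply is that little depends on this. The primary endpoint is PVR. The durability objective is also defined by PVR, at Weeks 24 and 48. PVR and time to PVF need a confirming event, which may fall after the window, so the single-record rule does not touch them. The snapshot is labelled a sensitivity analysis, no hypothesis is tested, and no contrast between visits is planned. Snapshot outcomes are listed by subject, so each subject classed as 50 or more can be identified. All of this stands, and it limits the point to minor.

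Four stronger readings are tempting, and the documents do not support them:

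- *The whole suppression trend shifts by construction.* With retests spread over 14-28 days, snapshot Weeks 12 and 48 differ by at most about 0.3 subject (3.2 − 2.9). Week 24 is the one that stands apart.
- *Week 12 looks worse than it should.* It does so only beside Week 24. Against the scheduled-visit value, the present rule makes Week 12 slightly more favourable, since 4-8% of elevations are overwritten.
- *Missing=Failure has the same step.* As SAP 6.2.2.5 specifies it, that table stops at Week 12, and Weeks 4, 8 and 12 have identical room. SAP 6.2.1 does list both missing-data methods at Weeks 24 and 48; the step would arise only if Missing=Failure were extended there.
- *A retest almost never counts at Weeks 4, 8 and 12, and never at Week 48.* The first depends on retest timing (40-60% in window if all are on day 14). The second has a rare exception in the snapshot: an unscheduled elevation from day 295 that is retested at the Week 48 visit.

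It is also fair to say that wide windows cut both ways. A value below 50 on day 168 followed by an unscheduled 50 or more on day 200 counts as 50 or more under the present rule.

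None of this removes the unequal treatment in Missing=Excluded and at snapshot Week 24, or the off-drug sample at Week 48.

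**Conclusion.** The point holds, as a minor one with a narrow scope. An isolated elevation is usually overwritten at Weeks 16, 24 and 36, usually retained at Weeks 4, 8 and 12, and retained in the Week 48 snapshot. This affects two outputs: the Missing=Excluded by-visit table, and the Week 24 snapshot read against Weeks 12 and 48. The SAP neither mentions nor corrects it.

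For an isolated elevation that re-suppresses, overwriting at Weeks 16 to 36 always moves the result towards apparent suppression. The size rests on a transient-elevation rate that the documents do not give; the assumed 1-5% yields about 0.6 to 3 of 64 subjects, or roughly 1 to 5 percentage points.

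The Week 48 problem in Missing=Excluded does not depend on that rate. For most completers who attend follow-up, the reported Week 48 value would be one taken off study drug.

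**What to change.** 1. In SAP 6.2.2.5, limit Missing=Excluded to on-treatment HIV-1 RNA (through last dose plus one day), matching the snapshot and CD4 analyses.
2. In SAP 3.7.3, for Missing=Excluded, select the sample labelled as the scheduled visit, and the record closest to the nominal day only if none is so labelled. The label should come first because a retest of the previous visit can lie nearer the nominal day than the scheduled sample. Use unscheduled retests only for PVR confirmation.
3. Keep the FDA last-in-window snapshot as specified. Add one supportive snapshot table at Weeks 12, 24 and 48 using the scheduled-visit value, and read any time trend from it.

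The cost is a few lines of SAP text and one table. Figures at Weeks 16 to 36 become slightly less favourable. A later unscheduled value of 50 or more in the same window would no longer count in these tables, although a confirmed one is still captured by PVR. The supportive table departs from the last-value convention and should be labelled accordingly.
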